12.1 Adverse Events

An adverse event (AE) with the date/time of onset, or that worsens in intensity, at or within 48 hours after the time of dosing with study drug will be considered a TEAE. AEs with a missing start date will be assumed to be treatment-emergent, except as described in Appendix 1. If a subject takes at least one dose of study drug, but the date and time of dosing is missing in the e-diary, all AEs for that subject will be considered treatment-emergent, if the AEs occur between available date of dosing as recorded only in CRF for up to 48 hours (2 days) post recorded date of dosing. If the date and time of the second dose is missing in e-diary then all AEs for that subject will be considered as treatment emergent due to second dose, if AEs occur between available date of dosing in CRF for second dose, and an ending boundary of 2 days after recorded date of dosing with second dose, inclusive. See Appendix 1 for derivations related to partial dates and times.

Nausea and/or vomiting reported as adverse events during a migraine by any subject that also noted these as characteristics of their migraine will be compared against placebo and may not be considered related to treatment but rather an underlying condition of the migraine.

AEs will be coded by the Medical Dictionary for Regulatory Activities (MedDRA) version 18.0.

Unless otherwise stated, frequencies of adverse events will be displayed by applicable treatment group and overall. AEs will be sorted alphabetically by system organ class (SOC) and then preferred term (PT) by frequency. For the overall summary of AEs, both subjects ever experiencing an event, as well as total events, will be presented. For all other summaries, subjects with multiple occurrences of the same AE preferred term will be counted once within the corresponding system organ class and preferred term.

Adverse events will be summarized in the following tables:

- Overall summary of AEs, including:
 - AEs
 - TEAEs
 - Related TEAEs
 - TEAEs leading to study discontinuation
 - Serious TEAEs
 - Related serious TEAEs
 - TEAEs leading to death
- Incidence of TEAEs
- Incidence of TEAEs by relationship to study drug
- Incidence of TEAEs by maximum severity
- Incidence of AEs leading to study discontinuation
- Incidence of related AEs leading to study discontinuation
- Incidence of TEAEs leading to death
- Incidence of serious TEAEs
- Incidence of serious TEAEs by relationship to study drug
- Incidence of serious TEAEs by maximum severity

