### **10.8.1 Adverse Events**

AEs will be coded by the Medical Dictionary for Regulatory Activities (MedDRA) preferred terms, and all summary tables for AEs will be organized by these categories. Frequency counts and percentages will be presented for subjects with AEs within each system organ class and preferred term, separated by treatment arm and treatment sequence and dose (the first dose and the second dose for recurrence or rescue or alternative rescue medication). Both subjects ever experiencing an event as well as total events will be presented. Descriptive statistics will

also be calculated for each treatment arm and treatment sequence and dose (initial and second dose for recurrence or rescue medication) for AE relationship and AE severity. If multiple intensities are reported for a given AE for a subject, the most severe intensity will be counted. A separate, similar analysis will be conducted for TEAEs.

An AE with the date of onset on or within 48 hours after a dose of study drug, or an event that worsens in intensity within 48 hours of a dose of study drug will be considered a TEAE. An AE that occurs in the interval after 48 hours of dosing until **EoS/Visit 2** will not be considered a TEAE.

SAEs and TEAEs that resulted in termination of the study drug and withdrawal from the study will be presented.

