 - a. Similarly for subjects who report a first dose time with start in the future (by several hours) than indicated dosing with question “Treating Migraine with Study Med now” as “Y” at the migraine pain begin time, their efficacy assessments for first dose will be those many hours ahead of the actual assessment time for severity reporting. For example, e-diary’s 0.5 hour time point is actually 7.5 hours if the first dose time is after 7 hours of the reported migraine start time. If the reported dose time is less than 10 minutes than the time of reporting migraine as in the stated question, then these will be ignored and subject’s efficacy assessments will be used for appropriate populations of efficacy analysis. All other subjects with time difference of greater than 10 minutes will be excluded from the appropriate populations of efficacy analysis.
9. Subjects with partial second dose time on CRF and no e-diary date and time for second dose Subjects who are able to enter the first dose assessment data in e-diary but they are not able to complete the e-diary for second dose. These subjects will be able to give second dose confirmation date on the CRF at site for visit 2 but may not remember the time of the dosing for second dose after first dose. These subjects will be considered in the appropriate populations of efficacy analysis for first dose available assessments based on the assumption that they took the second dose after the minimum of 2 hours post first dose. For these subjects any assessments for first dose data after 2 hours will be unscheduled and not be summarized. To rule out this assumption, these subjects will be removed from additional sensitivity analysis as described in Section 11.6 for primary and key secondary analysis.

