12 SAFETY ANALYSIS

This section details the specifications for summarizing safety endpoints.

Adverse event analyses will be presented on both the Safety and Safety-2nd Dose populations. Summaries on the Safety population will only include data up to the time of dosing with a second dose, and will be presented based on the first dose taken. Summaries on the Safety-2nd Dose population will only include data on or after the time of dosing with a second dose, and will be presented based on treatment sequence.

Laboratory, vitals, ECG, and C-SSRS analyses will be presented on the Safety population. These analyses will be presented by treatment sequence.

Safety endpoints will be summarized using descriptive or counts and percentages, as appropriate.

Values for all safety endpoints will also be presented in listings sorted by treatment group, site, and subject.

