16.2 PARTIAL DATE IMPUTATION: Algorithm for Treatment Emergence of Adverse Events

Imputed dates will not be presented in the listings

• START DATE/TIME	• STOP DATE/TIME	• ACTION
• Known	• Known	
 If start date/time < dose date/time, then not TEAE. 
 If start date/time ≥ dose date/time and < (dose date/time + 48 hours (or 2 days)), then TEAE
•	• Partial	
 If start date/time < dose date/time, then not TEAE.

• START DATE/TIME	• STOP DATE/TIME	• ACTION
		
 • If start date/time \geq dose date/time and $<$ (dose date/time + 48 hours (or 2 days)), then TEAE.
•	• Missing	
 • If start date/time $<$ dose date/time, then not TEAE. • If start date/time \geq dose date/time and $<$ (dose date/time + 48 hours (or 2 days)), then TEAE.
• Partial, but known components show that it cannot be on or within 48 hours after dose date/time	• Known	• Not TEAE.
•	• Partial	• Not TEAE.
•	• Missing	• Not TEAE.
• Partial, could be on or within 48 hours after dose date/time	• Known	
 • If stop date/time $<$ dose date/time, then not TEAE. • If stop date/time \geq dose date/time, then TEAE.
•	• Partial	
 • Impute stop date/time as latest possible date/time (e.g. last day of month if day unknown or 31st December if day and month are unknown), then: 
 • If stop date/time $<$ dose date/time, then not TEAE. • If stop date/time \geq dose date/time, then TEAE.
•	• Missing	• Assumed TEAE.
• Missing	• Known	
 • If stop date/time $<$ dose date/time, then not TEAE.

• START DATE/TIME	• STOP DATE/TIME	• ACTION
		
 If stop date/time \geq dose date/time, then TEAE.
•	• Partial	
 Impute stop date/time as latest possible date/time (e.g. last day of month if day unknown or 31st December if day and month are unknown), then: 
 • If stop date/time $<$ dose date/time, then not TEAE. • If stop date/time \geq dose date/time, then TEAE.
	Missing	
 Assumed TEAE.

16.3 DATA HANDLING RULES OF EFFICACY AND EXPLORATORY ANALYSIS FOR E-E-DIARY AND CRF DATES AND TIMES

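### For a second dose missing from the e-diary, SAP 12.1 sets the TEAE window by CRF calendar date (72 h) and does not say whether this or the 48-hour rule prevails

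*SAP*

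**What the plan says.** Four places tie treatment emergence to the time of the dose.

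- The opening sentence of SAP 12.1 covers an AE with onset, "or that worsens in intensity, at or within 48 hours after the time of dosing with study drug will be considered a TEAE".
- SAP Section 12 separates the AE tables by dose: "Summaries on the Safety-2nd Dose population will only include data on or after the time of dosing with a second dose".
- SAP Appendix 16.2, for an AE with a known start, says "If start date/time < dose date/time, then not TEAE". It counts a later start only if it falls before "dose date/time + 48 hours (or 2 days)), then TEAE".
- Protocol 10.8.1 sets the same end. "An AE that occurs in the interval after 48 hours of dosing until" the end-of-study visit is not a TEAE.

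The fallback later in SAP 12.1 works by date. If the e-diary lacks the date and time of the second dose, "all AEs for that subject will be considered as treatment emergent due to second dose, if AEs occur between available date of dosing in CRF". The window that it sets has "an ending boundary of 2 days after recorded date of dosing with second dose, inclusive".

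Two other parts of the SAP bear on this. Section 5 has sites record dose dates and times on the CRF for every subject, and lets CRF data stand in for missing e-diary dose dates in safety analyses. Section 5.4, Scenario 9, foresees subjects who can give the date of the second dose but "may not remember the time of the dosing for second dose after first dose". For efficacy, it assumes that their second dose came no sooner than 2 hours after the first.

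**The concern.** The fallback sentence names no clock time and does not itself require that onset or worsening follow the dose. It also ends later than the general rule. The SAP does not say whether the fallback overrides the time-based rules or yields to them, nor whether a recorded CRF time should be used. Two programmers could derive different second-dose flags from the same data.

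The safety of the second dose is a stated objective (Protocol 5.4), and AEs are tabulated separately by dose to serve it. Under the fallback, the TEAE definition for a second dose depends on whether the e-diary captured that dose. Where the CRF gives only a date, events of the first dose can be shown as events of the second.

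**Working it through.** **Inputs.** The fallback window runs from the CRF date D to D+2, inclusive (SAP 12.1). The general window is 48 h from the dose time (SAP 12.1, first sentence; the Protocol 10.8.1 limit agrees). The second dose is allowed from 2 to 24 h after the first (SAP 4.1), so both can fall on one date. Let t be the clock hour of the second dose, from 0 to 24.

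**Step 1: length of the fallback window.** D, D+1 and D+2 make 3 dates × 24 h = 72 h. The excess over the general rule is 72 − 48 = 24 h, one third of the window. If D+2 were excluded, the window would be 2 × 24 = 48 h, but the text includes it. Appendix 16.2 applied to dates (start on or after D and before D + 2 days) covers 2 dates.

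**Step 2: where the excess lies.** The part before the dose is t. The part after the dose is 72 − t, of which 72 − t − 48 = 24 − t lies past the 48-hour limit. The sum t + (24 − t) = 24 h does not depend on t.

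| Second dose at | Before the dose (h) | Window closes after the dose (h) | Past 48 h (h) |
|---|---|---|---|
| 08:00 | 8 | 64 | 16 |
| 12:00 | 12 | 60 | 12 |
| 20:00 | 20 | 52 | 4 |

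**Step 3: CRF time recorded.** The Section 12 restriction can be applied, and it removes the t hours before the dose from the second-dose tables. It sets no end, so 72 − t h remain after the dose and the last column stands. For example, an AE starting 55 h after a noon dose is not a TEAE if the e-diary holds the dose, but is one under the fallback if it does not. If the general rule or Appendix 16.2 governed instead, the window would be 48 h with nothing before the dose.

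**Step 4: CRF date only.** Section 12 has no time to filter on. Appendix 16.2 deals with partial AE dates and takes the dose date/time as given. As an illustration, take a first dose at 09:00 on D and a second dose on D at an unknown time. An AE starting at 09:30 lies inside the fallback window and is labelled a second-dose TEAE. Under the Scenario 9 assumption the second dose was not taken before 11:00, so this AE preceded it. SAP 12.1 makes no such assumption for AEs. An AE at 14:00 cannot be ordered either way.

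**The case against.** The strongest reply is that the SAP already requires an event to follow the dose: in the first sentence of 12.1, in Section 12 and in Appendix 16.2. This stands. A reader might infer that the SAP has no such rule, or that AEs before the second dose enter the second-dose tables even when its time is recorded. The documents support neither. The silence is in the fallback sentence and in the lack of an order of precedence.

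Using a recorded CRF time is also the more natural reading. Section 5 takes the first recorded dose date and time for the safety baseline whatever its source, and Appendix 16.3 uses the CRF time of an unrecorded second dose to cut off first-dose efficacy data. Neither passage settles 12.1.

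A third reply is that a date-level window is cautious, since CRF dosing data rest on recall. With only a date known, D to D+2 is the shortest run of whole dates sure to cover 48 h. This stands for the date-only case, and the fix keeps that end. It does not justify the longer end when a time is recorded. Caution may justify calling an event treatment-emergent, but not assigning it to the second dose.

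Nor is the 48-hour limit uniform elsewhere. Appendix 16.2 counts some AEs with missing or partial start dates whose onset may lie past 48 h, the first-dose fallback is also dated from the CRF, and Protocol 9.2.2 gives no time limit. So this is not the only way a later AE can be counted.

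Finally, a reader might infer bias between sequences, because active first doses produced more AEs than placebo in Phase 2. Those rates, in Protocol 4.2, are overall rates and not rates between doses. Sequences that share a first dose have, by randomisation, the same expected first-dose background. No such bias is shown.

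**Conclusion.** The point holds as a minor inconsistency, in two parts. With a recorded CRF time, the fallback counts AEs that start after 48 h and up to 72 − t h after the dose, contrary to Protocol 10.8.1 and Appendix 16.2. With a CRF date only, AEs that began after the first dose but before a second dose on the same date are labelled second-dose TEAEs. Those AEs lie within 48 h of the first dose and are TEAEs either way, so what changes is the dose to which they are attributed.

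The 24 h excess follows from the text and rests on reading the end date as included. The number of subjects affected is not given, so the effect on AE counts cannot be sized. Only descriptive second-dose AE tables are touched. The documents show no efficacy effect.

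**What to change.** Replace the second-dose fallback sentence in SAP 12.1 with:

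> If the second dose is not in the e-diary but its CRF date and time are recorded, an AE is a second-dose TEAE if it starts, or worsens in intensity, at that time or up to 48 hours later. If only the CRF date is known, the window opens at the later of 00:00 on that date and first dose + 2 h (as in Scenario 9), unless other data show that the second dose was taken earlier. It closes at the end of the second day after that date. AEs with onset before the window opens and no later worsening are reported under the first dose if they meet the first-dose TEAE rule. AEs whose order relative to the second dose cannot be determined are counted as second-dose TEAEs and flagged in the listing.

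The cost is one SAP paragraph and a change to the derivation of the second-dose TEAE flag, with no new table. CRF dose dates and times (SAP Section 5) and AE start times (Protocol 9.2.1) are already collected.

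The fix has limits. It relies on recalled CRF times. In the date-only case, among AEs that start after the first dose, it moves only those starting in the first 2 h; later ones on that date stay counted, with a flag. If a second dose was taken early and nothing shows it, an AE caused by that dose could be assigned to the first.

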12.1.1 Relationship to Study Drug

Summaries of AEs by relationship to study drug will classify AEs as either:

- Reasonably or Possibly Related
- Not Reasonably or Possibly Related

Related AEs are those that are recorded on the AE CRF page as “Reasonably or Possibly Related” or those with a missing relationship.

12.1.2 Adverse Event Severity

Severity of AEs will be classified as one of the following:

- Mild
- Moderate
- Severe
- Life-threatening

If multiple severities are reported for a given adverse event for a subject, the highest severity reported will be used. Any adverse event with missing severity in the locked data base will not be summarized by severity.

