## **9.2 Adverse Events and Serious Adverse Events**

### **9.2.1 Adverse Events**

An AE is defined as any undesirable physical, psychological, or behavioral effect experienced by a subject during his/her participation in an investigational study, in conjunction with the use of the drug, whether or not product-related. During the treatment of a migraine with study drug subjects will be asked if they are feeling anything unusual that they have not felt with a migraine before. A 'yes' response will trigger an alert to the site to contact the subject and assess the AE in terms of what the subject is experiencing, how long the symptoms lasted and how much the symptom(s) impacted them. During the time between dosing, subjects will be asked how they are feeling. A response of 'not well' will trigger an alert to the site to contact the subject and assess the AE similarly to the assessment of AEs reported during treatment. The occurrence of AEs should be sought by non-directive questioning of the subject at each visit in the study. AEs may include, but are not limited to:

- Subjective or objective symptoms spontaneously offered by the subject and/or observed by the Investigator or medical staff, and
- Changes in laboratory abnormalities that are clinically relevant as assessed by the Investigator and for which a medical intervention was initiated.

Disease signs, symptoms, and/or laboratory abnormalities already existing prior to the use of the product are not considered AEs after treatment unless they reoccur after the subject has recovered from the pre-existing condition or, in the opinion of the Investigator; they represent a clinically significant exacerbation in intensity or frequency. AEs are collected from the time the subject signs the informed consent form until the completion of **EoS/ Visit 2**. AEs reported prior to dosing will be captured and considered non-treatment emergent AEs. AE reported 48 hours after dosing until the completion of **EoS/Visit 2** will be captured and considered non-treatment emergent AEs.

All AEs must be recorded in the site's study records and the AE CRF with the following information:

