1. Relationship to Study Drug: The Investigator must assess whether they consider an AE to be drug-related. In assessing this relationship, the Investigator must use information about the drug as outlined in the Investigator's Brochure (IB), the subject's pre-existent medical conditions/concurrent medication, and chronology of the event relative to drug administration. The following definitions will be used:

- **Reasonably or possibly related** applies to those AEs that, after careful medical consideration at the time they are evaluated, are considered by the Investigator (or other qualified physician) to have at least a possible relationship to study drug.
- **Not reasonably or not possibly related** applies to those AEs that, after careful medical consideration at the time they are evaluated, are considered by the Investigator (or other qualified physician) to have no relationship, or no reasonable possibility of a relationship, to study drug.

2. Event Severity: The Investigator will be asked to assess the severity of the AE using the WHO Toxicity Criteria, as shown in [Appendix 1](#). The WHO criteria assign a grade of 1 through 4 to indicate the severity of AEs. For AEs that are not listed in the WHO criteria, the Investigator will use medical judgment to assess the severity of the AE.

The following are guidelines to be used by the Investigator to judge the event severity of an AE that is not in the WHO Toxicity Criteria:

- Mild - awareness of sign or symptom, but easily tolerated
- Moderate - discomfort enough to cause interference with usual activity
- Severe - incapacitating with inability to work or perform usual activity
- Life Threatening

3. Duration: Start and end dates and times, or if continuing.
4. Action taken.
5. Whether it constitutes a SAE, per definition below.
6. Outcome: resolved, resolved/ with sequelae, continuing, death, or unknown (only for subjects that are lost to follow-up).

The investigator (or designee) should attempt to establish a diagnosis of the AE based on the sign, symptoms and/or other clinical information. In such cases, the diagnosis, and not the individual signs/symptoms or laboratory abnormalities should be documents in the subject's source documentation and the CRF unless the etiology of the event is unknown. An assessment should be made at each visit (or more frequently if necessary) of any changes in severity, the suspected relationship to study drug, the interventions required to treat it and the outcome.

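### Adverse events with severity still missing at database lock drop out of the maximum-severity tables with no row or count to show it, so severity can be understated; the likely effect is small

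*SAP*

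**What the plan says.** SAP 12.1.2 sets four severity classes (mild, moderate, severe, life-threatening) and two rules. Where grades differ, "If multiple severities are reported for a given adverse event for a subject, the highest severity reported will be used". Where there is no grade, "Any adverse event with missing severity in the locked data base will not be summarized by severity". The SAP provides no Missing row, footnote, imputation or sensitivity table for such events.

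Two outputs listed in SAP 12.1 depend on severity: "Incidence of TEAEs by maximum severity" and "Incidence of serious TEAEs by maximum severity". Under SAP Section 5, percentages use all subjects in the summarized population of each treatment group unless otherwise specified, and nothing in 12.1.2 changes that.

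Other gaps in AE data are resolved towards more harm. SAP 12.1.1 defines related events as those recorded as related "or those with a missing relationship". SAP 12.1 states that "AEs with a missing start date will be assumed to be treatment-emergent", subject to the exceptions in the appendix. SAP 12.1.4 counts an event as serious if the general seriousness item is ticked, even when no specific criterion is.

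On collection, Protocol 9.2.1 says "All AEs must be recorded in the site's study records and the AE CRF with the following information", and severity is the second item on that list: "The Investigator will be asked to assess the severity of the AE using the WHO Toxicity Criteria". Protocol 10.8.1 plans severity summaries using the most severe intensity and does not mention leaving out ungraded events.

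**The concern.** For a missing relationship or start date, the SAP takes the reading less favourable to the drug. For a missing severity it takes the event out of the table, and no reason is given for the difference. Because the denominator does not change, removal has the same effect on a percentage as if the event had not happened.

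Two consequences follow when a grade is missing. A subject whose only event is ungraded disappears from the table. A subject with one mild and one ungraded event is shown as mild, whatever the second event was. The severity rows then need not add up to the TEAE total, and no count explains the gap.

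At stake is the descriptive severity profile. No hypothesis test depends on it. More events are expected on lasmiditan, so at equal missing rates most dropped events would come from those arms. In the serious-TEAE table, where counts are likely to be small, one dropped event could be noticeable.

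**Working it through.** The plan states no figure on this point, so there is none to reproduce.

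**Direction.** Suppose a subject has an ungraded event.

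- If it is the only event, the subject leaves the table and the denominator is unchanged.
- If there is also a graded event, the subject is placed at the graded level. That is right if the ungraded event was no worse, and too low if it was worse.

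The number of subjects at or above any given grade can therefore fall but cannot rise. A lower row taken alone, such as mild, can gain a subject who belonged in a higher one. The mild-plus-ungraded case arises only within one preferred term or in a row that pools terms, because 12.1.2 takes the highest grade for a given event.

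**Inputs.**

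- Subjects per arm: 570 treated (Protocol 5.5; SAP 2.1).
- TEAE rates r: 22% placebo, 65% on 50 mg, 73% on 100 mg, 86% on 200 mg (Phase 2, Protocol 4.2).
- Share m of subjects with a TEAE whose grade is missing: assumed 1 to 5%, one event per subject.
- Share s of TEAEs that are severe: assumed 5 to 20%, equal across arms.

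**Subjects affected = 570 × r × m.**

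| Arm | With a TEAE | m = 1% | m = 3% |
|---|---|---|---|
| Placebo | 570 × 0.22 = 125.4 | 1.3 | 3.8 |
| 50 mg | 570 × 0.65 = 370.5 | 3.7 | 11.1 |
| 100 mg | 570 × 0.73 = 416.1 | 4.2 | 12.5 |
| 200 mg | 570 × 0.86 = 490.2 | 4.9 | 14.7 |

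The lasmiditan share is (370.5 + 416.1 + 490.2) / 1402.2 = 91%. Three of the four arms are lasmiditan, so equal TEAE rates would already give 75%.

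**Understatement of severe incidence = r × s × m, if missingness is unrelated to severity.** Ranges are for s = 5 to 20%, in percentage points.

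| m | 200 mg | Placebo |
|---|---|---|
| 0 | 0 | 0 |
| 1% | 0.04 to 0.17 | 0.01 to 0.04 |
| 3% | 0.13 to 0.52 | 0.03 to 0.13 |
| 5% | 0.22 to 0.86 | 0.06 to 0.22 |

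As an outer bound, if every ungraded event were severe, the loss is r × m. On 200 mg that is 0.86 points at m = 1% and 2.58 at 3%; on placebo it is 0.22 and 0.66.

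**Comparison between arms.** With equal m and s, the ratio is 0.86 × s × (1 − m) / [0.22 × s × (1 − m)] = 3.91 for any m. Only the absolute difference shrinks, by the factor (1 − m).

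**Possible handling rules, at m = 1% and s = 10%, 200 mg minus placebo:**

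- All grades known: (0.86 − 0.22) × 10% = 6.40 points.
- SAP rule: 6.40 × 0.99 = 6.34, an error of about 0.06.
- Missing counted as Severe: 6.34 + 0.64 × 1% = 6.98, an error of about 0.58.

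Under these assumptions the second error is (1 − s)/s times the first: 9 times at s = 10%, 19 times at 5% and 4 times at 20%.

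**The case against.** The best defence is that the rule may never apply. Severity is a required AE item. Protocol 11.2 describes automatic validation checks, and Protocol 12 provides for queries, makes the monitor responsible for complete eCRFs, and places lock after the database is declared complete and accurate. This stands, and it is why the effect has to be stated conditionally. It does not make the rule redundant. The SAP itself provides for grades missing at lock, and SAP Section 6 has disposition rows for loss to follow-up and for treated subjects who do not return for Visit 2.

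It can also be said that nothing is hidden. The exclusion covers only summaries by severity. The events still count in the overall AE, incidence, relationship, serious and discontinuation tables, and all safety values are listed (SAP 12). This also stands. What is missing is a count in the severity tables that explains why their rows fall short.

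A further argument is that the contrast with relationship is not a contradiction. Relationship has two categories and one obvious conservative default. Severity has four, and the literal worst case would be life-threatening. That is fair: the documents do not conflict, but the severity rule is out of line with its neighbours and unexplained.

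Three stronger readings are tempting and lack support:

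- A reader might infer that maximum severity is understated as a matter of fact. The documents give no rate of missing grades, and an ungraded event matters to maximum severity only if it was the subject's worst or only one.
- A reader might infer a relative bias in favour of lasmiditan. With equal missingness and severity mix the ratio is unchanged, and the documents give no reason to expect unequal missingness.
- A reader might infer that serious events would be lost. Protocol 9.3 and 9.4 require reporting within 24 hours and follow-up to resolution or stability, and an ungraded serious TEAE still appears in the other serious-event tables.

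**Conclusion.** The point holds as a minor reporting gap. If any grade is missing at lock, the two maximum-severity tables can understate severity, cannot overstate the number of subjects at or above a given grade, and need not reconcile with the TEAE total.

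The effect is zero if nothing is missing. At an assumed 1 to 3% ungraded it reaches about 5 to 15 subjects on 200 mg and 1 to 4 on placebo. If missingness is unrelated to severity and 5 to 20% of TEAEs are severe, severe incidence on 200 mg is too low by about 0.04 to 0.5 points.

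These sizes rest on Phase 2 TEAE rates carrying over, 570 dosed per arm, one event per subject, and assumed missing and severe shares that appear nowhere in the documents. The concentration in the lasmiditan arms is one of absolute counts.

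A reader might also conclude that missing severity should simply be counted as Severe in the main table, to match the rule for relationship. The calculation does not support that: if missingness is unrelated to severity, it overstates the difference between arms by more than the SAP rule understates it. It belongs in a supportive summary.

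**What to change.** In SAP 12.1.2, replace the exclusion with wording such as: *AEs with missing severity will be kept in the by-severity tables in a separate Missing row by treatment group; if any are present, a supportive summary of maximum severity will count them as Severe, with the number so classified in a footnote.*

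So that the rows add up, the table shell should place each subject once: under the highest reported grade if there is one, and under Missing only if every event contributing to that row is ungraded. The footnote should also count ungraded events among subjects shown at a reported grade.

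The cost is one SAP sentence and one table row, settled before unblinding. If grades are missing, there is also one supportive table, whose severe column may be slightly higher and may overstate severe events. If nothing is missing, the Missing row is empty and the supportive table is not produced.
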